9.2.4 Serious Adverse Event Collection Timeframe

SAEs must be recorded from the time of signature of Patient Informed Consent through 30 days after completion of the last dose. The onset date of the SAE is defined as the date the event meets serious criteria. The resolution date is the date the event no longer meets serious criteria, the date the symptoms resolve, or the event is considered chronic. In the case of

hospitalizations, the hospital admission and discharge dates are considered the onset and resolution dates, respectively.

In addition, any signs or symptoms experienced by the subject prior to study entry or leading up to the onset date of the SAE or following the resolution date of the SAE, must be recorded as an AE, if appropriate.

9.2.5 Serious Adverse Event Onset and Resolution Dates

The onset date of the SAE is defined as the date the event meets serious criteria. The resolution date is the date the event no longer meets serious criteria, the date the symptoms resolve, or the event is considered chronic. In the case of hospitalizations, the hospital admission and discharge dates are considered the onset and resolution dates, respectively.

In addition, any signs or symptoms experienced by the subject prior to study entry or leading up to the onset date of the SAE or following the resolution date of the SAE, must be recorded as an AE, if appropriate.

9.2.6 Fatal Outcome

Any SAE that results in the subject's death (i.e., the SAE was noted as the primary cause of death) must have fatal checked as an outcome with the date of death recorded as the resolution date. For all other events ongoing at time of death that did not contribute to the subject's death, the outcome should be considered not resolved, without a resolution date recorded.

For any SAE that results in the subject's death or any ongoing events at the time of death, the action taken with the investigational product should be recorded as "dose not changed" or "not applicable" (if the subject never received investigational product).

9.2.7 Regulatory Agency, Institutional Review Board, Independent Ethics Committee, and Site Reporting

The Sponsor is responsible for notifying the relevant regulatory authorities/US central Institutional Review Boards (IRBs) of related, unexpected SAEs.

In addition, the Sponsor (or designee) is responsible for notifying active sites of all related, unexpected SAEs occurring during all interventional studies across the program.

The Investigator is responsible for notifying the local IRB, or the relevant local regulatory authority of all SAEs that occur at his or her site as required.

10. DATA MANAGEMENT AND STATISTICAL METHODS

10.1 Data Collection

The Investigators' authorized site personnel must enter the information required by the protocol on the eCRF. A study monitor will visit each site in accordance with the monitoring plan and review the eCRF data against the source data for completeness and accuracy. Discrepancies between source data and data entered on the eCRF will be addressed by qualified site personnel. When a data discrepancy warrants correction, the correction will be made by authorized site personnel. Data collection procedures will be discussed with the site at the site initiation visit and/or at the Investigator's Meeting (if applicable). It is expected that site personnel will complete the eCRF entry within five business days of the subject's visit.

10.2 Clinical Data Management

Data collected in the eCRF will follow certain pre-set standards. Quality control and data validation procedures are applied to ensure the validity and accuracy of the clinical database.

Data are to be reviewed and checked for omissions, errors, and values requiring further clarification using computerized and manual procedures. Data queries requiring clarification are to be communicated to the site for resolution. Only authorized personnel will make corrections to the clinical database, and all corrections are to be documented in an auditable manner.

10.3 Statistical Analysis Process

Details regarding the statistical methods and definitions will be provided in the Statistical Analysis Plan (SAP). The SAP will be finalized prior to unblinding to preserve the integrity of the statistical analysis and study conclusions. All statistical analyses will be performed after the database is locked and unblinded. Statistical analyses will be performed using Version 9.1 or higher of SAS® (SAS Institute, Cary, NC 27513).

10.4 Subject Disposition

Subjects in each analysis set, as well as subjects who complete the study, and subjects who prematurely discontinue from the study will be summarized by treatment group using descriptive statistics. In addition, for subjects who prematurely discontinue from the study, the reasons for discontinuation will be summarized by treatment group.

10.5 Demographic and Baseline Characteristics

Descriptive summaries of demographic and baseline characteristics will be presented by treatment group and overall for the Safety Analysis Set and Full Analysis Set.

Demographics and baseline characteristics will be examined to assess the comparability of the treatment groups at baseline. Continuous variables such as subject age, weight, height, and body mass index (BMI) will be summarized using number of observations, mean, standard deviation, median, minimum, and maximum values. Categorical variables such as subject sex and race will be summarized using number of observations and percentages for each category.

Medical history will be summarized by treatment group using the number of observations and percentages of subjects reporting each category.

10.6 Investigational Product Exposure

Summary statistics for the duration of exposure to investigational product will be presented by treatment group. The number of subjects receiving each dose will be summarized by treatment group and by visit in the study. Compliance rates will be summarized by treatment group at each visit.

10.7 Prior and Concomitant Medication

Sites must maintain adequate records of concomitant medications and procedures throughout the study. Prior and concomitant medications will be coded using the World Health Organization (WHO) drug dictionary. Prior and concomitant medications will be listed and summarized by preferred drug name and treatment group.

10.8 Safety Analyses

Adverse events will be coded using MedDRA. The number of events, incidence, and percentage of treatment-emergent adverse events (TEAE) will be calculated overall, by system organ class (SOC), and by preferred term. Treatment-emergent adverse events will be further summarized by severity and relationship to the investigational product. Adverse events related to the investigational product, AEs leading to withdrawal, SAEs, and deaths will be summarized/listed.

Clinical laboratory tests, vital signs, and ECG findings will be summarized by treatment group and visit. Potentially clinically important findings will also be summarized or listed.

10.9 Efficacy Analysis

All efficacy endpoints are considered secondary endpoints. Descriptive statistics for efficacy endpoints will be reported at 3, 6, 12, 24, 48 and Follow-Up Visit (at termination) as well as Week 0 and Week 6 (or 8) for IV to oral transition patients.

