In clinical trials of HFpEF, pharmacologic treatment has been largely neutral; only exercise training and weight loss appear to improve exercise intolerance and quality of life. (8) ESC guidelines in treatment of PH-HFpEF subjects acknowledge that the accepted treatment target is reduction of pulmonary wedge pressures using diuretics for congestion. However, clinical studies have demonstrated neutral results with identified concerns that PH-targeted therapies could have detrimental effects due to rapid increases in LV filling pressures, resulting in acute pulmonary edema. Thus, the ESC guidelines specify that there are currently no established strategies to treat pulmonary vascular disease (PVD) and right ventricular disease (RVD) in HFpEF, with a recommendation (class III) not to use approved PAH treatments in PH-HFpEF subjects. (4,9). With no demonstrated effective therapy, these subjects have a poor outcome (5 yr. survival $< 50\%$, frequent hospitalizations). (10)

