2.2.2 Secondary Objectives

The study will evaluate whether the effectiveness of intermittent (weekly) levosimendan and daily oral levosimendan (based on patient transition) is sustained in extended use.

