3.4 Withdrawal of Subjects

A subject may withdraw from the study at any time for any reason without prejudice to their future medical care by the physician or at the institution. The Investigator or Sponsor may withdraw the subject at any time (e.g., in the interest of subject safety). The withdrawal of a subject from the investigational product by the Investigator should be discussed where possible with the Medical Monitor and/or Sponsor before the subject stops investigational product.

If the investigational product is discontinued, regardless of the reason, the final evaluations are to be performed as completely as possible. Whenever possible, all discontinued subjects should also undergo the protocol-specified Follow-Up Visit (at termination) evaluations. Comments (spontaneous or elicited) or complaints made by the subject must be recorded in the source documents. The reason for termination, date of stopping investigational product, and the total amount of investigational product taken must be recorded on the Case Report Form (eCRF) and source documents.

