3.1.4 Summary Statistics

Categorical data will generally be summarized with counts and percentages of patients. The denominator used for the percentage calculation will be clearly defined. Continuous data will generally be summarized with descriptive statistics including n (number of non-missing values), mean, median, standard deviation, minimum, and maximum.

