3.4.2 Secondary Endpoints

The secondary endpoints (Efficacy measures) of the study are:

- 6-minute walk test score (6MWT),
- Patient global assessment score (based on the KCCQ instrument),
- Physician's Assessment of Functional Class (measured by NYHA Functional Class assessment), and
- Incidence of clinical events (death and hospitalizations).

All Secondary Endpoint measurements will be presented in patient-level listings.

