3.5 Primary Endpoint Assessment

Primary endpoint safety measures will be summarized by treatment/dose group and overall using descriptive statistics (number of observations, mean, median, standard deviation, minimum, maximum) for continuous variables and counts and percentages for categorical data. Summaries will be based on the SAF. Associated patient-level listings will also be provided for the primary endpoint safety measures. Primary endpoint efficacy measures will not be summarized but will be provided in patient-level listings.

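### The protocol promises by-visit efficacy summaries, the SAP gives only listings, and neither says how death or withdrawal counts, so sustained effectiveness would be read from patients still in the study

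*Protocol*

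**What the plan says.** **Objective.** Protocol 2.2.2 asks whether the effectiveness of weekly IV and daily oral levosimendan "is sustained in extended use". SAP 2.1.2 restricts this to oral dosing. Patients who stay on IV are followed for two years from entry (Protocol 1.1), and those who transition for three years afterwards (Protocol 4.3).

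**Method in the protocol.** Section 10.9: "Descriptive statistics for efficacy endpoints will be reported at 3, 6, 12, 24, 48 and Follow-Up Visit (at termination"), plus Week 0 and Week 6 or 8 for transition patients. Yearly visits are not named there, although Protocol 2.3 schedules yearly efficacy assessments.

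**Method in the SAP.** Section 3.1.4: "Continuous data will generally be summarized with descriptive statistics including n (number of non-missing values"). Section 3.4.2: "All Secondary Endpoint measurements will be presented in patient-level listings". Section 3.5 adds: "Primary endpoint efficacy measures will not be summarized but will be provided in patient-level listings". That sentence is oddly worded, because the primary endpoints are safety measures. The table list runs from 14.1.x to 14.3.x with no efficacy table; 6MWT, KCCQ and NYHA class appear as Listings 16.2.6.1 to 16.2.6.3. SAP 3.4 nevertheless speaks of efficacy analyses in the SAF and in a PP set that SAP 3.2 does not define.

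**Exits.** Protocol 3.4.1 lists adverse event, lack of efficacy and withdrawal by subject, among others. Protocol 5.4.1 adds catheter complications and Attachment 3 adds stopping rules. On discontinuation: "Whenever possible, all discontinued subjects should also undergo the protocol-specified Follow-Up Visit (at termination) evaluations" (Protocol 3.4). Death is part of a separate secondary endpoint, "Incidence of clinical events (death and hospitalizations") in SAP 3.4.2, and Protocol 10.8 has deaths summarised or listed.

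**The concern.** A patient who dies, or who stops for an adverse event or lack of efficacy, is one in whom benefit was not sustained. Without a rule for such exits, that patient is absent from every later scheduled visit. The visit statistics can then hold steady or improve because the patients doing worst have gone. There is no control arm in which the same selection would show.

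The two documents also disagree on what will be produced. The protocol promises summaries that the SAP does not contain. Whoever makes them later has no rule to follow, and a reader of the listings alone has no defined denominator. The question at stake is the only one that the efficacy data are collected to answer.

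**Working it through.** There is no design figure to reproduce: the study has no sample size calculation and SAP 3.1.5 rules out hypothesis testing. The check has two parts.

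**1. Is there a rule anywhere?** The SAP's imputation text covers medication dates (3.3.4), the last oral dose date (3.3.5) and adverse event dates (3.5.1). Nothing covers a 6MWT, KCCQ or NYHA value that is absent because of death, withdrawal or a missed visit. Protocol section 10 has no such rule either. Available-case reporting is thus the default; it follows from this silence and from the non-missing count in SAP 3.1.4, and is not stated as a choice.

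**2. How much could it matter?**

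*Inputs from the documents*
- 5-year survival below 50% (Protocol 1.2).
- Parent-study 6MWD difference 29.3 m, 95% CI 2.5 to 56.1; mean change +16.6 m on levosimendan (Protocol 1.3.5).
- 18 and 19 patients randomised in the parent study, 37 in all (Protocol 1.3.5). No N is given for this study.

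*Assumptions*
- Constant hazard.
- 5-year survival S5 of 50%, with 70% for a fitter, selected cohort.
- Normal walk changes, with the six-week SD carried forward.
- A correlation ρ between leaving and poor walk change.

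*SD of 6MWD change.* SE = (56.1 − 2.5)/(2 × 2.030) = 13.2 m. SD = 13.2/√(1/18 + 1/19) = 40.1 m. The implied p is 0.033, against the protocol's 0.0329, so these inputs agree with each other.

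*Proportion dead.* Hazard h = −ln(S5)/5 per year, which is 0.1386 at 50% and 0.0713 at 70%. Proportion dead f = 1 − exp(−ht).

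| Time | S5 = 50% | S5 = 70% |
|---|---|---|
| Week 48 | 12.0% | 6.4% |
| 1 year | 12.9% | 6.9% |
| 2 years | 24.2% | 13.3% |
| 3 years | 34.0% | 19.3% |

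If all 37 had enrolled, 50% survival would mean about 4.4 deaths by week 48, 9.0 by 2 years and 12.6 by 3 years.

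*Shift in the observed mean change.* Shift = ρ × SD × φ(z)/(1 − f), where z is the normal quantile of f and φ the normal density.
- S5 = 50%, 1 year: φ/(1 − f) = 0.2109/0.871 = 0.242. The shift is 2.9 m at ρ = 0.3 and 4.9 m at ρ = 0.5.
- S5 = 50%, 3 years: 0.3665/0.660 = 0.555. The shift is 6.7 m and 11.1 m.
- S5 = 70%, 3 years: 0.2737/0.807 = 0.339. The shift is 4.1 m and 6.8 m.
- ρ = 0: no shift at any time.

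*Effect of counting death.* Suppose survivors hold the parent-study change of +16.6 m with SD 40.1 m. A survivors-only summary shows +16.6 m at every visit. With death ranked worst, the overall median is 16.6 + 40.1 × z((0.5 − f)/(1 − f)), where z(·) is the normal quantile. At S5 = 50% this is +9.7 m at week 48, +0.1 m at 2 years and −11.5 m at 3 years. At S5 = 70% it is +13.2, +8.8 and +4.4 m.

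**The case against.** The strongest reply is that the SAP plans no visit means at all. It lists the data, so no mean can drift upwards. That is right about the SAP, and a reader who inferred that the SAP will report survivors-only means would be wrong. But Protocol 10.9 still promises the statistics, and SAP section 4 claims no deviation from the protocol. It cites v5.0, while the protocol available is v4.1, so a later change to 10.9 cannot be excluded.

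Second, one might infer that every leaver vanishes. The documents do not support this. Patients who leave alive should have a termination visit whenever possible; it includes 6MWT, KCCQ and NYHA class, and 10.9 reports it. This stands as a real mitigation. However, that visit pools patients at very different times, supplies nothing to later scheduled visits and cannot cover deaths.

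Third, deaths (Protocol 10.8) and reasons for discontinuation (SAP 3.3.1) are reported elsewhere, and the n at each visit would show attrition. True, but not by visit beside the efficacy values, and the SAP's table list has no dedicated output for deaths or hospitalisations.

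Fourth, the survival figure describes patients without effective therapy. This cohort consists of haemodynamic responders who completed the parent study and passed renal, hepatic and other exclusions, so its mortality may well be lower. That is accepted, and is why 70% is shown.

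Finally, efficacy here is secondary, descriptive and untested, in what the parent study suggests is at most 37 patients. That limits the consequence.

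**Conclusion.** The point holds in this form: the protocol and SAP disagree on whether efficacy is summarised, and neither handles death or withdrawal for 6MWT, KCCQ or NYHA class. A statement that effectiveness was sustained would rest on those still in the study. Termination visits and separate death reporting lessen this without correcting it.

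The size is illustrative. Deaths of 12%, 24% and 34% at week 48, 2 years and 3 years (50% survival), or 6%, 13% and 19% (70%), rest on a constant hazard. The shifts of 3 to 5 m at 1 year and 7 to 11 m at 3 years (4 to 7 m at 3 years at 70% survival) also rest on a correlation of 0.3 to 0.5 that neither document supplies, and on a six-week SD. The 2- and 3-year shifts apply to yearly visits, which 10.9 does not name. A reader might go further and take the extreme case, in which leavers have exactly the lowest values (9.7 m at 1 year, 22.3 m at 3 years), as the expected bias, or the background survival as this cohort's mortality. The documents support neither. With no correlation the mean does not shift, although patients who died would still go uncounted in a claim of sustained benefit.

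**What to change.** Reconcile Protocol 10.9 with SAP 3.4.2 and the SAP table list by adding one descriptive table per dosing period (IV, oral) and visit, including yearly visits.

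1. **Accounting.** Of all who started the period, show the numbers assessed, dead, withdrawn by reason, missed, and ended by planned transition or administrative closure.
2. **Summary over all starters.** Count death and withdrawal for adverse event or lack of efficacy as not sustained. Two options are the median change with death ranked worst, or the percentage alive, on study drug and not worse than at period start for 6MWD, KCCQ and NYHA class. State any 'not worse' margin in advance, because with a zero margin measurement noise alone would class many stable patients as worse.
3. **Planned transition.** Treat the IV-to-oral transition as the administrative end of the IV period, not as a failure. Protocol 2.5 and 4.3 transition all consenting patients, so scoring it as a failure would build bias into the IV summary.
4. **Label.** Mark any visit statistics 'observed patients only'.

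The cost is one SAP paragraph and one descriptive table from data already collected. No test or alpha is affected. The downside is a little more analysis work and a less favourable figure for sustained benefit.

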Body Weight	X	X					X	X
Serum Chemistry and Hematology (Local Lab) ⁷	X	X			X ⁶	X	X	X
Child Pugh Class ⁷	X							X
Vital Signs	X	X	X	X	X	X	X	X
Pharmacokinetic Sample		X ²		X	X ²	X ²		
Electrocardiogram (ECG)	X	X			X ⁶	X		X
Levosimendan Administration (oral) / Dose Titration ³		X	X	X	X ⁴			
NYHA Functional Class	X	X			X ⁶	X	X	X
6 - Minute Walk Test	X	X			X ⁶	X	X	X
Adverse Events/SAEs ⁸	X	X	X	X	X	X	X	X
Concomitant procedures and medications	X	X	X	X	X	X	X	X
KCCQ Assessment ⁹	X	X			X ⁶	X	X	X

Footnotes for Time and Events Schedule

1. Visits will be scheduled 7-9 days following completion of the levosimendan IV dose and every 14 days through the oral levosimendan transition (+/- 48 hrs); at the Investigator's discretion, Week 2 and 4 visits may be performed remotely.
2. Blood sample to be taken prior to the patient's daily dose of oral levosimendan.
3. The first dose of oral levosimendan to be taken 7-9 days after the patient's final weekly IV levosimendan dose. Once oral levosimendan begins, subjects must completely discontinue weekly levosimendan infusions. Patients will begin a daily dose regimen of 1mg daily and titrated at 1mg increments every 2 weeks, as tolerated.
4. At the investigator's discretion, patients that have not demonstrated an adequate response to drug therapy and a tolerance to the 1mg levosimendan TID may be titrated to 1mg QID. Patients that have not tolerated 1 mg levosimendan TID should be down titrated to 1mg BID. All patients that are titrated at Week 6 should return for a Week 8 visit.
5. Due to the COVID-19 pandemic, the investigator may have a phone conversation with the patient rather than having the patient come in for an office visit. The phone conversation should include the following, as reported by the patient; adverse events, concomitant medications (new or changed), concomitant procedures, and blood pressure & heart rate (use provided home blood pressure cuff).
6. If a patient is up or down titrated and therefore scheduled for a Week 8 visit, these procedures do not need to be performed at Week 6.
7. Local labs will be drawn (including NT-proBNP). Child-Pugh Class is only required for patients with documented liver disease.
8. During routine visits and throughout a participation in the study, patients should be queried for any new or changes to AEs, concomitant medications, concomitant procedures, hospitalizations, and/or emergency room visits

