2.5 Investigational Product

Upon entry into the study, levosimendan was administered in open-label, intravenously at 0.075 µg/kg/min for 24 hours ±30 min, or as per directed by the treating physician. A physician was to assess the patient's safety at Week 3 and up-titrate to 0.1 µg/kg/min for 24 hours. The decision to increase the dose was to be based on the absence of disease or drug related adverse events and the investigator's discretion.

If a subject was down-titrated to 0.05 µg/kg/min in the TNX-LVO-04 study for either the Lead-In dose or during the double-blind portion of the study, the subject was to start at this dose, with the first opportunity to up-titrate following at Week 3.

All subjects will be transitioned to an oral dose of levosimendan once an informed consent form has been signed. Those currently receiving levosimendan IV weekly will return to the investigational site and receive 1mg levosimendan capsule daily for two weeks.

Subjects may then be titrated up every 2 weeks at 1mg levosimendan increments up to maximum of 4 mg daily (1mg QID), based on assessments of safety and patient's clinical response (see [Attachment 3 Cardiac Event Recommendations and Management](#)). Patients that tolerate 3 mg (1mg TID) oral levosimendan TID that have not demonstrated a 6MWD equivalent or better than the recorded 6MWD at initiation of their IV to oral levosimendan may be titrated to 4 mg (1mg QID). Patient's that experience identified safety concerns in Attachment 3 should be downtitrated at 1 mg/day increments or discontinued at the physician's discretion.

Once a patient completes the transition to oral levosimendan, all IV drug and ancillary supplies related to the administration of IV levosimendan will be returned to the central pharmacy for destruction.

At the initial visit of the IV to oral levosimendan transition, each patient will receive a supply of 1mg oral levosimendan capsules. Subsequent supplies may be shipped to the patient's home.

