2.2.3 Study Drug and Dosing Regimen

All patients entering the study will continue receiving intravenous (IV) levosimendan weekly, and some of them will be transitioned to an oral dose of levosimendan. Those currently receiving IV levosimendan weekly will return to the investigational site and receive 1mg levosimendan capsule daily for two weeks.

Patients may then be titrated up every 2 weeks at 1mg levosimendan increments up to maximum of 4 mg daily (1mg QID), based on assessments of safety and patient's clinical response. Patients who tolerate 3 mg (1mg TID) oral levosimendan TID that have not demonstrated a 6MWT equivalent or better than the recorded 6MWT at initiation of their IV to oral levosimendan may be titrated to 4 mg (1mg QID). Patients who experience identified safety concerns in should be down-titrated at 1 mg/day increments or discontinued at the physician's discretion.

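### The transition efficacy time point in protocol 10.9 is Week 6 or Week 8, chosen partly by the patient's own walk result, and the Week 6 walk that the choice needs is waived in titrated patients

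*Protocol*

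**What the plan says.** - **Reported time point.** Protocol 10.9 gives descriptive efficacy statistics at the office visits "as well as Week 0 and Week 6 (or 8) for IV to oral transition patients". It has no rule for which week enters when a patient has both. Section 7.1.5 treats the final evaluation of the transition as being at one week or the other.
- **Walk-based route to Week 8.** Protocol 2.5 says of patients who tolerate the TID step: those "that have not demonstrated a 6MWD equivalent or better than the recorded 6MWD at initiation of their IV to oral levosimendan may be titrated". The step in question is QID. SAP 2.2.3 repeats the rule.
- **Other wording of that route.** Footnote 4 of the schedule and Section 5.5.1 do not name the walk: "At the investigator's discretion, patients that have not demonstrated an adequate response to drug therapy" but tolerate TID may be titrated.
- **Route not based on the walk.** "Patients that have not tolerated 1 mg levosimendan TID should be down titrated to 1mg BID".
- **Who has Week 8.** "All patients that are titrated at Week 6 should return for a Week 8 visit" (footnote 4).
- **Waiver.** Footnote 6 says that, for a patient titrated up or down and therefore "scheduled for a Week 8 visit, these procedures do not need to be performed at Week 6". The schedule attaches this footnote to the 6MWT, KCCQ and NYHA class, and to the physical examination, ECG and laboratory tests. Section 7.1.4 nevertheless lists the 6MWT, KCCQ and NYHA class at Week 6. Section 7.1.5 prints a waiver of these three and the physical examination under the Week 8 visit without saying which week is waived.
- **SAP output.** Section 3.1.2 assigns visits as recorded on the CRF. Section 3.4.2 puts all secondary endpoints in patient-level listings. The list of outputs has Listing 16.2.6.1 for the 6MWT and no efficacy table. Section 3.1.5 rules out hypothesis tests.

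**The concern.** Patients who walk at least as far as at Week 0 keep their Week 6 value. Some of those who walk less far are titrated and measured again two weeks later. If the later value stands in for the earlier one, low readings caused by test noise get a second chance and high readings do not, so the mean moves upward.

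The waiver adds a direct contradiction. The Section 2.5 decision needs a Week 6 walk, yet footnote 6 says the walk need not be done in the patients for whom the decision is made. Read literally with 7.1.5, a titrated patient could lack a walk at either week.

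At stake is the secondary objective, whether effectiveness is sustained on oral drug. The later office visits are counted from entry into TNX-LVO-05 (Sections 2.3.1 and 7.1.5), so Week 0 against Week 6 or 8 is the only efficacy contrast scheduled around the change of route. There is no control arm in which the same bias would cancel. Week 8 values also follow a dose change and two more weeks of treatment, so a mixed mean does not estimate one quantity.

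**Working it through.** The documents give no sample size, margin or threshold for this endpoint, so there is no design figure to reproduce. The spread comes from the parent-study result in protocol 1.3.5.

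**1. SD of 6MWD change**
- Inputs: difference 29.3 m, 95% CI 2.5 to 56.1, p = 0.0329; 18 and 19 patients randomised; changes +16.6 m and -12.7 m.
- Difference: 16.6 + 12.7 = 29.3 m, as stated.
- SE = [(56.1 - 2.5)/2] / t(0.975, 35 df) = 26.8/2.030 = 13.2 m.
- Check: 29.3/13.2 = 2.22, p = 0.033, which agrees with the stated value.
- SD of change = 13.2/sqrt(1/18 + 1/19) = 13.2/0.329 = 40.1 m.

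**2. Bias of a mean in which Week 8 replaces poor Week 6 values**

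Let the changes from Week 0 be D6 = delta + e6 - e0 and D8 = delta + e8 - e0, with independent normal test errors of variance s². Let mu be the true mean change and f the fraction of patients with D6 < 0 who are titrated up. Given D6, the expected value of D8 - D6 is -(s²/SD²)(D6 - mu). Averaging over D6 < 0 gives

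bias = f × (s²/SD) × phi(mu/SD), where phi is the standard normal density.

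If a share h of the change variance is test noise, then s² = h × SD²/2, and at mu = 0

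bias = f × h × (40.1/2) × 0.399 = 8.0 × f × h metres.

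| Case, no true change | Bias |
|---|---|
| All variance is noise (s = 28.4 m), all eligible patients titrated | +8.0 m |
| Same, with 20% of patients down-titrated regardless of the walk | +6.4 m |
| Half the variance is noise, all eligible titrated | +4.0 m |
| All variance is noise, half of eligible titrated | +4.0 m |
| All variance is noise, a quarter of eligible titrated | +2.0 m |
| Week 6 walk not done in titrated patients | 0 |

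The last row is zero because a walk that was not done cannot select on its own error. A simulation of 2,000,000 patients gave 8.05 m for the first row. With all eligible patients titrated, the share at or above Week 0 rises from 50% to 67% (all noise) or 62% (half noise).

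**3. If benefit is truly lost on oral drug** (f = 1, h = 1, the worst case above)
- True change -16.6 m, the parent-study gain on levosimendan: bias +7.4 m, shown as about -9.2 m.
- True change -29.3 m, the whole between-arm difference: bias +6.1 m, shown as about -23 m.
- Largest loss fully hidden: the x that solves x = 20.07 × phi(x/40.1), which is 7.9 m.
- Hiding the full -16.6 m would need s of about 60 m, and hiding -29.3 m about 106 m, against at most about 28 m implied by step 1.

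**The case against.** The strongest reply is that the biased mean may never be computed. The SAP keeps visits as recorded, lists the 6MWT by patient, has no efficacy table and tests nothing. Protocol 10.9 does not say that the two weeks are pooled, and its phrase may be visit shorthand. This stands and lowers the weight of the point. It does not remove it. Protocol 10.9 still commits to descriptive statistics, SAP section 4 claims no deviation from the protocol (citing v5.0, while the protocol supplied is v4.1), and a listing cannot show a Week 6 walk that was waived.

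Second, the link to the walk is partial. Up-titration is permitted rather than required, two sections leave it to the investigator's view of response, and intolerance also leads to Week 8. This stands and is why the bias is given as a range.

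Third, the two parts pull against each other: if the walk is waived, this selection bias is zero. That also stands, and it sets the lower end of the range.

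A reader might go further and infer that the mixed time point would make oral levosimendan appear to maintain 6MWD even if it did nothing. The documents do not support that. The 8 m figure assumes no true change from Week 0, in which case distance really is maintained. If the parent-study benefit were lost, the summary would still show a decline of about 9 to 23 m.

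**Conclusion.** The point holds as a moderate one. The contradiction between Section 2.5 and footnote 6, with the unclear waiver in 7.1.5, is plain on the page and needs no calculation. The outcome-dependent choice of week is real but partial. If a 10.9 summary is made with Week 8 replacing poor Week 6 values, it is tilted toward maintained by 0 to about 8 m, at most 27% of the 29.3 m parent-study difference (8.0/29.3).

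The range assumes normal, independent test errors, no learning effect or trend, no effect of the extra dose step between Weeks 6 and 8, and a parent-study SD that carries over to the transition. The share of variance due to test noise and the fraction titrated are not in the documents and were varied. The number of transitioned patients is not stated, but the expected bias does not depend on it.

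It might be tempting to treat this as undermining the study's conclusions. The endpoint is secondary and descriptive in an open-label study whose primary objective is safety, with no test and no threshold for sustained effect, so that reading goes too far.

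**What to change.** 1. Remove the 6MWT, KCCQ and NYHA class from the footnote 6 waiver, so that every transitioned patient has them at transition Week 6. Make 7.1.5 name the week to which any remaining waiver applies.
2. In protocol 10.9 and the SAP, report Week 6 for all transitioned patients as the fixed time point. Report Week 8 separately, for titrated patients only, as change from their own Week 6. With one week for everyone, the selection bias in the main summary is zero. The Week 8 change in up-titrated patients still contains regression to the mean (up to about 16 m in the first case of the table, from -32 m to -16 m), so it should not be read as an effect of the dose step.
3. Reconcile 2.5, footnotes 4 and 6, 5.5.1 and 7.1.5 on what information the Week 6 decision uses. No dose rule needs to change for this.
4. State in the SAP whether the 10.9 summary will be produced.

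If some Week 6 walks have already been skipped under the waiver, show them as missing, with the count, rather than filling them from Week 8. State that the Week 6 mean then leaves out titrated patients.

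The cost is a few wording changes and, in titrated patients, one Week 6 walk, questionnaire and NYHA class assessment. Section 7.1.4 already lists all three, and Section 2.5 already needs the walk.
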